4.3 Randomization, blinding and treatment allocation

Subjects will be randomly assigned to one of four treatment arms, either 1000 mg Vitamin E, 1.89 g DHA EE, 1000 mg Vitamin E + 1.89 g DHA EE, or placebo (PBO) based on a computergenerated randomization scheme, i.e. interactive-web-based response system (IWRS). Subjects will be stratified by Diabetes, Type II diagnosis (in no greater than 50% of sample). Enrolment will be competitive across study sites.

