9.3.3 Secondary endpoint variable(s) and analyses

- Differences in hepatic fat fraction [%], measured by MRI-PDFF after 6 months of intervention, between DHA and placebo will be estimated with the same model as the primary endpoint. The estimated difference will be displayed with its 95% confidence interval.
- Differences in hepatic fat fraction [%], measured by MRI-PDFF after 6 months of intervention, between Vitamin E and placebo will be estimated with the same model as the primary endpoint. The estimated difference will be displayed with its 95% confidence interval.
- Between group differences in anthropometric measures, after 3 and 6 months of DHA EE and/or Vitamin E intervention will be analysed with the same approach as the primary endpoint, using the relevant anthropometric measure at baseline as the respective baseline covariate and gender as a categorical covariate.
- Between group differences in inflammatory markers after 6 months of intervention and liver enzymes after 3 and 6 months of DHA EE and/or Vitamin E intervention will be analysed with the same approach as above and diabetes status as a categorical covariate included in the model.
- Between group differences in the FIB-4 score after 6 months of DHA EE and/or Vitamin E intervention will be analysed with the same approach as above.
- \circ Between group differences in plasma DHA and plasma α -tocopheryl after 3 and 6 months of intervention will be analysed with the same approach as above.
- Between group differences in SF-36 quality of life score after 6 months of DHA EE and/or Vitamin E intervention will be analyzed by ANCOVA with baseline score included in the model.
- Between group differences in dietary intake of LC-PUFA (i.e. DHA and EPA) will be assessed by the FFQ and analysed over time by repeated measures ANOVA with baseline level and site included in the model.

With blinded data, the residuals of the models will be analysed visually (QQ-plots, residual plots) to determine if the model assumptions (normality, variance homogeneity) are met. If necessary, variance-stabilizing transformations or non-parametric methods will be considered.

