# 7.0 Determination of Sample Size and Randomization

As indicated in section 9.3.7 of the study protocol, with 60 subjects per arm for the combination (DHA EE + vitamin E) and PBO groups, there is 80% power to detect a 3.64% absolute reduction in liver fat assuming a standard deviation of 7% and a two-sided 0.05 significance level with a two-sample t-test (G\*power 3.1.9.2). To estimate the secondary endpoints of the PBO compared to the components (DHA EE, vitamin E) with a given precision of ±3% of liver fat, a total of 30 subjects per arm are needed for the

DHA EE and the vitamin E groups. Accounting for an expected 10% attrition, the resulting required sample size was 200 subjects.

Subjects will be randomly assigned to one of four treatment arms following an unequal allocation of 65/65/35/35 for combination (DHA EE + vitamin E), PBO, DHA EE, and vitamin E, respectively. A computer generated randomization scheme (i.e. interactive web based response system [IWRS]) will be used to assignment stratified by Type II diabetes.

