#### 8.2 Primary Endpoint Analysis

The 6-month hepatic fat fraction [%] will be evaluated with a linear mixed analysis of covariance (ANCOVA) model. Baseline hepatic fat fraction [%], intervention group, and baseline diabetes status will be included as fixed effects. Study site will be included as a random effect. The residuals of the model will be analyzed visually (QQ-plots, residual plots) to verify model assumptions (normality, constant variance, homogeneity) are met. If necessary, a variance stabilizing transformation (i.e. log) may be considered. The impact of the random effect will be evaluated with the likelihood ratio test and may be removed if not significantly adding to the model. The model derived pairwise comparison between the combination (DHA EE + vitamin E) and PBO will be estimated using least squares means and tested for significance with a t-test. Since the primary outcome is the pre-specified comparison of DHA EE + vitamin E compared to PBO at 6-month, no adjustment for multiple comparisons is planned.

Note that the estimate of the treatment effect is computationally identical to an analysis that utilizes the change score (6-month vs. baseline) as the response variable adjusted for baseline, intervention group, and baseline diabetes status as fixed effects and site as a random effect. However, the 6-month response variable was selected to allow for easier variance stabilizing transformations if necessary.

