The differences between intervention groups (DHA EE + vitamin E vs. PBO, vitamin E vs. PBO, DHA EE vs. PBO) in dietary intake of LC-PUFA, specifically DHA and EPA, will be assessed over time with a linear mixed model following an ANOVA approach. Fixed effects will include the intervention group, categorical time point (baseline, 1 month, 3 months, 6 months), and intervention group by time point interaction. A random intercept and a random time effect for subject nested within site will be included. For the random time effect, the covariance structure (e.g compound symmetry, unstructured) will be selected such that the AICC (corrected Akaike information criterion) is reduced. If a significant interaction effect is indicated, an interaction plot will be produced and the relevant pairwise comparisons between intervention groups and PBO at each time point (i.e. DHA EE + vitamin E vs. PBO, vitamin E vs. PBO, DHA EE vs. PBO) will be estimated along with a 95% confidence interval (CI) at each modeled time point. The Benjamini-Hochberg (false discovery rate) adjustment will be used for the 12 planned comparisons. Additionally, the model derived change from baseline to each follow-up time point will be estimated along with a 95% confidence interval.

For each model, the residuals of the model will be analyzed visually (QQ-plots, residual plots) to verify model assumptions (normality, constant variance, and homogeneity) are met. If necessary, a variance stabilizing transformation may be considered. The impact of the random effect(s) will be evaluated with the likelihood ratio test and may be removed if not significantly adding to the model.

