# 8.4 Exploratory Endpoint Analyses

The interaction between intervention groups and each of PNPLA3, HSD17b, and haptoglobin SNPs, as well as with the specified categorical demographic and baseline variables (section 4.3), on the 6-month hepatic fat fraction will be evaluated with the model specified in the primary endpoint analysis (section 8.2) where the interaction between intervention group and respective variable (i.e. SNP, categorical variable) will also be included. A separate model for each will be constructed for each exploratory interaction. Pairwise comparisons of DHA EE + vitamin E vs. PBO, vitamin E vs. PBO, and DHA EE vs. PBO will be estimated for each genotype / category along with 95% confidence intervals and presented in forest plots.

Transcriptomics (Tx) analysis of the PBMC gene expression will follow a discovery approach. The analyses will be performed internally at DSM. In brief, the gene expression workflow will be performed as defined by the Partek Software (https://www.partek.com/). The large data set will be first visually explored using different techniques like heat maps, clustering and principal component analysis (predefined by the Tx software application). This will also trigger the thresholds to be used in further processing. ANOVA pairwise group comparisons (placebo vs the different treatments) will be applied with the goal to identify genes that are significantly differently expressed. The contrast method of Fisher's least significant difference (LSD) will be used (Gene expression workflow, Partek Software) and q-Values (FDR) will be calculated to correct for multiple testing. The q-values will be set after inspection of the whole Tx data set, but will be between q = 0.05 - 0.15, if possible. The filtering will use the change fold of +1.2 fold up- and -1.2 fold down regulation versus the placebo group with the lowest p-values

2017-1088 (PUVENAFLD) SAP Version 4.0

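### The dietary DHA/EPA model omits the type II diabetes stratum that the SAP's other written-out between-arm models include, so its per-visit intervals may be slightly wider than needed

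*SAP*

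**What the plan says.** Type II diabetes is the only stratification factor that the documents name. Protocol 4.3 sets it, with a cap of half the sample, and SAP 7.0 says that the computer-generated scheme "will be used to assignment stratified by Type II diabetes".

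The SAP's models mostly follow the design. For the primary endpoint, SAP 8.2 states: "Baseline hepatic fat fraction [%], intervention group, and baseline diabetes status will be included as fixed effects". The component-arm contrasts use that same model. The 3- and 6-month secondary model, the 6-month secondary model (both SAP 8.3) and the ELF/Pro-C3 model (SAP 8.5) each list diabetes. The SNP and subgroup models and the oxylipin model (SAP 8.4) take it over by reference to the primary model.

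The dietary DHA/EPA model in SAP 8.3 differs. Its fixed effects are given in full: "Fixed effects will include the intervention group, categorical time point (baseline, 1 month, 3 months, 6 months), and intervention group by time point interaction". The random part is also specified: "A random intercept and a random time effect for subject nested within site will be included". Per-visit comparisons are conditional: "If a significant interaction effect is indicated, an interaction plot will be produced and the relevant pairwise comparisons" follow only then, with a Benjamini-Hochberg adjustment over 12 comparisons (3 arms against placebo at 4 time points). Changes from baseline are estimated as well. In Protocol 9.3.3, dietary intake is "analysed over time by repeated measures ANOVA with baseline level and site included in the model", again without diabetes.

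The transcriptomic analysis in SAP 8.4 is only summarized: "ANOVA pairwise group comparisons (placebo vs the different treatments) will be applied with the goal to identify genes that are significantly differently expressed". No covariate is named.

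**The concern.** When randomization is stratified, the arms are balanced on the stratum by design. A model that leaves the stratum out still estimates the arm difference without bias. However, any variance that the stratum explains is counted as noise, so standard errors are overstated and tests are conservative.

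The dietary model is more exposed to this than the ANCOVA models. There, a baseline covariate would already absorb much of a stable difference between diabetic and non-diabetic subjects. In the dietary model, baseline is one of the response time points, so no other fixed effect takes up such a difference and it goes into the between-subject variance.

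At stake is some precision in a supportive secondary output, and consistency with the rest of the SAP. There is no bias and no inflated error rate.

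**Working it through.** **The plan's own figure.** The one calculated size in the plan reproduces. For a difference of 3.64, SD 7, two-sided alpha 0.05 and 80% power, the exact two-sample t-test gives 60 per arm (power 0.806), and 180 / 0.90 = 200. It concerns liver fat and has no bearing on the dietary model.

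**Inputs from the documents.** Stratification by diabetes, at most 50% diabetic (Protocol 4.3; SAP 7.0); allocation 65/65/35/35 (SAP 7.0); fixed and random effects of the dietary model (SAP 8.3); two-sided alpha 0.05 (SAP 8.0).

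**Assumed input.** R², the share of the variance in intake at one visit that diabetes explains. The documents give no value. The range used is 0 to 0.10, with 0.25 as an extreme.

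**Step 1: arm difference at one visit.** With arms balanced on the stratum:

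- width ratio, unadjusted to adjusted = 1 / √(1 − R²)
- actual type I error of one contrast = 2 × [1 − Φ(1.96 / √(1 − R²))]

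| R² | Width ratio | Excess width | Actual alpha |
|---|---|---|---|
| 0 | 1.000 | 0% | 0.050 |
| 0.01 | 1.005 | 0.5% | 0.049 |
| 0.05 | 1.026 | 2.6% | 0.044 |
| 0.10 | 1.054 | 5.4% | 0.039 |
| 0.25 | 1.155 | 15.5% | 0.024 |

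The alpha column is for a single contrast taken alone, before the interaction gate and the Benjamini-Hochberg step.

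**Step 2: change from baseline.** Write subject i's intake at time t in arm a as y = μ(a,t) + δ·D + b + e, where D is diabetes status and b the subject intercept. In the 6-month value minus baseline, δ·D and b both drop out. A diabetes effect on level alone therefore cannot affect the arm difference in change, nor the group-by-time test built on such differences.

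**Step 3: simulation check.** 4,000 trials, 65/65/35/35, 50% diabetic in each arm, random subject intercept, diabetes shifting the level only. Mean standard error of one 65-versus-65 contrast:

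| R² | 6-month difference, without / with stratum | Difference in change, without / with stratum |
|---|---|---|
| 0 | 0.1751 / 0.1751 | 0.1749 / 0.1749 |
| 0.05 | 0.1798 / 0.1752 | 0.1752 / 0.1752 |
| 0.10 | 0.1848 / 0.1751 | 0.1749 / 0.1750 |

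At R² = 0.10 the ratio is 0.1848 / 0.1751 = 1.055, in line with Step 1. The difference in change does not move.

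**Step 4: gene expression, about 40 subjects in 4 arms.** Residual degrees of freedom fall from 36 to 35. Let R² here be the share of the residual sum of squares that the term removes in the sample. The width ratio, unadjusted to adjusted, is t(0.975, 36) / [t(0.975, 35) × √((1 − R²) × 36/35)]. This gives 0.985 at R² = 0, 0.998 at 0.026, 1.011 at 0.05 and 1.038 at 0.10. Below about 0.03 the extra term widens the interval slightly; above that it narrows it.

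**The case against.** The case for leaving the model alone is fair in several respects.

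- **The size may be zero.** Nothing in the documents shows that diabetes predicts DHA or EPA intake. Intake is capped at entry by the FFQ, and fatty fish and supplements are restricted (Protocol 5.6), which limits the spread that any factor could explain. This stands, and is why the point is stated conditionally. A reader might infer that the intervals are certainly too wide; the documents do not support that.
- **The protocol's dietary model has no diabetes term either**, so the SAP did not drop a pre-specified adjustment. This stands. The mismatch is with the design and the SAP's other models.
- **The main dietary results are untouched.** A reader might infer that the omission makes a drift in background omega-3 intake between arms harder to detect. Drift is the group-by-time interaction and the change from baseline, and a diabetes level effect cancels from both. Only the per-visit contrasts can tighten, and they are produced only after a significant interaction.
- **No power loss can be read off.** A reader might turn the width ratio into a fall from 80% power. No dietary or gene-expression contrast is powered in the plan; the 80% refers to liver fat.

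A reader might also extend the point to gene expression and infer that its results are too imprecise or distorted by diabetes. That is not supported. SAP 8.4 describes the workflow only in summary, so diabetes is unstated rather than excluded. It plans gene lists with q-values and fold-change filters, and no intervals. The outcome is change from baseline (SAP 4.3), which removes a stable diabetes effect. Chance imbalance in a subset taken from the first 55 randomized is possible, but the documents give nothing to show that it would affect expression change.

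None of this supplies a reason for the dietary model to differ from the others.

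**Conclusion.** The point holds as a minor inconsistency in one secondary model. The dietary DHA/EPA model leaves out the randomization stratum without explanation. Its per-visit arm-versus-placebo intervals may therefore be 0% to about 5% wider than needed, with mildly conservative tests.

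That range rests on an assumed R² of 0 to 0.10, on arms balanced for diabetes among subjects with FFQ data, and on diabetes shifting the level of intake only. If diabetes altered the time course of intake, the interaction test and the changes could also be affected, but the documents give no sign of this. The primary analysis is unaffected. The gene-expression ANOVA is at most a matter of missing detail.

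**What to change.** In SAP 8.3, in the paragraph on dietary intake of LC-PUFA, add diabetes stratum to the fixed effects, so that they are intervention group, time point, their interaction, and diabetes stratum. The cost is one degree of freedom, which is negligible with 200 randomized subjects, and one change of wording. Stratum is recorded at randomization, so no new data are needed.

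For the transcriptomic ANOVA in SAP 8.4, no change is required. If the section is edited anyway, one sentence could say whether diabetes is a factor; with about 40 subjects either choice is defensible.

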|         |             | Q1, Q3            |     |                       |        |           |

Supplement table for outcomes analyzed with repeated measures ANCOVA collected at baseline, 3-month, and 6-month

The following table will serve as a guide for the repeated measures ANOVA outcomes (i.e. dietary intake of DHA and EPA) collected at baseline, 1-month, 3-month, and 6-month. As specified in the SAP, the pairwise comparisons will only be conducted if there is a significant interaction effect. Additionally, an interaction plot will be produced. Note, a supplemental table will be created to provide descriptive statistics for the absolute and percent change from baseline.

|          |   | РВО | DHA EE +
vitamin E | DHA EE | vitamin E |
|----------|---|-----|-----------------------|--------|-----------|
| Baseline | N   |     |                       |        |           |
|          | mean (sd)                                   |     |                       |        |           |
|          | median (min, max)                           |     |                       |        |           |
|          | Q1, Q3                                      |     |                       |        |           |
| 1-Month  | N   |     |                       |        |           |
|          | mean (sd)                                   |     |                       |        |           |
|          | median (min, max)                           |     |                       |        |           |
|          | Q1, Q3                                      |     |                       |        |           |
| 3-Month  | N   |     |                       |        |           |
|          | mean (sd)                                   |     |                       |        |           |
|          | median (min, max)                           |     |                       |        |           |
|          | Q1, Q3                                      |     |                       |        |           |
| 6-Month  | N   |     |                       |        |           |
|          | mean (sd)                                   |     |                       |        |           |
|          | median (min, max)                           |     |                       |        |           |
|          | Q1, Q3                                      |     |                       |        |           |

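### Dietary DHA and EPA are defined as 6-month differences from placebo, yet the SAP estimates those differences only after a significant 9-df interaction; the random-effects wording is also over-parameterised on its natural reading (minor).

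*SAP*

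**What the plan says.** SAP 4.2 places DHA and EPA intake among the measures to be compared at 6 months for three contrasts: combination, vitamin E and DHA, each against placebo.

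SAP 8.3 gives the model. Besides arm, its fixed effects are these: "categorical time point (baseline, 1 month, 3 months, 6 months), and intervention group by time point interaction". The random part reads: "A random intercept and a random time effect for subject nested within site will be included". Its structure is to be picked by an information criterion: "the covariance structure (e.g compound symmetry, unstructured) will be selected such that the AICC". SAP 8.3 also lets the analyst drop a random term when a likelihood ratio test finds no significant contribution from it.

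The between-arm output is conditional: "If a significant interaction effect is indicated, an interaction plot will be produced and the relevant pairwise comparisons between intervention groups and PBO". Estimates and intervals for every visit come only after that. The dietary shell in SAP 12.1 agrees: "the pairwise comparisons will only be conducted if there is a significant interaction effect". The multiplicity rule reads: "The Benjamini-Hochberg (false discovery rate) adjustment will be used for the 12 planned comparisons".

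One model-based output is not placed behind that condition: "Additionally, the model derived change from baseline to each follow-up time point will be estimated along with a 95% confidence interval".

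Protocol 9.3.3 plans a repeated measures ANOVA for dietary intake that includes baseline level and site. It states no interaction condition.

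**The concern.** The endpoint is a difference from placebo at one visit. The condition is a test of a different and broader hypothesis: that no arm's time profile departs from any other's at any visit. If that test fails, the difference that SAP 4.2 promises is not estimated. No other model-based secondary contrast in SAP 8.3 is conditioned in this way.

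The estimate is worth having. DHA is one of the study products. Protocol 5.6 prohibits omega-3 supplements and fortified foods and restricts fatty fish. Protocol section 1 notes that contamination of the placebo group limited an earlier omega-3 trial. An interval for arm-minus-placebo intake shows how large a dietary imbalance the data can exclude; a non-significant interaction does not.

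The second issue is the covariance. There is one questionnaire per visit, and two subject-level random terms plus a residual may ask for more variance parameters than four repeated values can supply.

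**Working it through.** **The SAP's own count.** Three contrasts with placebo × 4 time points = 12 comparisons, as stated. Three of the 12 are at baseline. Interaction degrees of freedom: (4 − 1) × (4 − 1) = 9.

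**Probability that the condition is met**

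Inputs from the documents: allocation 65/65/35/35 and 10% attrition (SAP 7.0), giving 58.5/58.5/31.5/31.5 after multiplying by 0.9, total 180; two-sided 0.05 (SAP 8.0). Assumed, because the documents give nothing: equal correlation ρ between visits, and a drift d = 0.4 SD at 1, 3 and 6 months in one arm only.

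- Interaction noncentrality: λ = d² × n(1 − n/180) × 0.75/(1 − ρ). The 0.75 is the centred sum of squares of the drift pattern (0, 1, 1, 1), that is 3 − 9/4.
- Combination, ρ = 0.5: 0.16 × 58.5 × 0.675 × 1.5 = 9.48. Against the 9-df chi-square critical value of 16.92, the probability of significance is 54%.
- Vitamin E, ρ = 0.5: 0.16 × 31.5 × 0.825 × 1.5 = 6.24, giving 35%.
- Baseline-adjusted 6-month contrast: SE = √[(1 − ρ²)(1/n + 1/58.5)]. Combination: 0.160, so 0.4/0.160 = 2.50 and power is 70%. Vitamin E: 0.191, 2.09 and 55%.
- Unadjusted per-visit difference: SE = √(1/n + 1/58.5). Combination: 0.185, 2.16 and 58%. Vitamin E: 0.221, 1.81 and 44%.

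| Assumed ρ | Drifting arm | Interaction significant | Baseline-adjusted 6-month contrast | Unadjusted per-visit difference |
|---|---|---|---|---|
| 0.3 | combination | 38% | 62% | 58% |
| 0.3 | vitamin E | 25% | 48% | 44% |
| 0.5 | combination | 54% | 70% | 58% |
| 0.5 | vitamin E | 35% | 55% | 44% |
| 0.7 | combination | 80% | 86% | 58% |
| 0.7 | vitamin E | 58% | 72% | 44% |

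A second check used 60/60/30/30 completers and sized the drift so that the baseline-adjusted 6-month contrast had 80% power. With one arm drifting and ρ from 0.3 to 0.7, the interaction was significant in 38% to 69% of trials. With all three active arms drifting together the range was 55% to 89%.

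**Covariance parameters**

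Four visits give a 4 × 4 within-subject matrix with 4 × 5/2 = 10 distinct elements. Compound symmetry has 2: one variance and one covariance. With categorical random time:

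| Specification | Parameters | Estimable |
|---|---|---|
| Intercept + unstructured time + residual | 1 + 10 + 1 = 12 | 10 |
| Intercept + compound-symmetric time + residual | 1 + 2 + 1 = 4 | 2 |
| Same, intercept dropped | 11 or 3 | 10 or 2 |
| Intercept + time structure as the residual matrix | 11 or 3 | 10 or 2 |
| Time structure as the residual matrix only | 10 or 2 | 10 or 2 |
| Intercept + linear random slope + residual | 4 | 4 |

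The intercept adds a constant to every element and the residual adds a constant to the diagonal. Both named structures already contain both terms.

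**The case against.** **A reader might infer that dietary drift could go unreported, or that no interval would be shown.** The documents do not support this. Descriptive statistics by visit (SAP 8.0), absolute and percent change by arm (SAP 12.1), and the model-derived change from baseline with its interval (SAP 8.3) all sit outside the condition. Drift in one arm would be visible. What is lost is the model-based difference from placebo.

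**The power gap is smaller than it can be made to look.** A contrast averaging all three follow-ups against baseline reaches 75% and 60% at ρ = 0.5, but neither the SAP nor the fix below reports that contrast. Against the unadjusted per-visit difference the gap is 58 − 54 = 4 points (combination) and 44 − 35 = 9 (vitamin E). At ρ = 0.7 the interaction is the more powerful of the two. With a Bonferroni split over three contrasts, the unadjusted difference has 41% and 28%, below the interaction. This objection stands: power is not the main argument. The case for unconditional reporting is that the endpoint is an estimate.

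**The questionnaire is not the only evidence on contamination.** SAP 8.3 compares plasma DHA with placebo at 3 and 6 months without any condition, and SAP 6.5 sets plasma cutoffs that flag excess DHA in the placebo and vitamin E arms. Nothing says that a non-significant interaction will be read as absence of drift. Plasma levels cannot, however, separate diet from product in the two arms given DHA.

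**The covariance may be estimable.** The word categorical is attached to the fixed effect, the two structures are examples, and a linear slope would be identified. But choosing between compound symmetry and an unstructured matrix has little meaning for a single slope, so categorical random time is the natural reading. Removal by likelihood ratio test can drop the intercept; if a separate residual is kept, one surplus parameter remains.

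**Conclusion.** The point holds as a minor inconsistency. SAP 4.2 defines a 6-month difference from placebo; SAP 8.3 and its shell may not produce it. That conclusion needs no assumed numbers. The size does: at ρ = 0.5 with a sustained 0.4 SD drift in one arm, the difference would be estimated in about 54% of trials (combination) or 35% (vitamin E), and the figures move substantially with ρ and with the pattern of drift.

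The covariance wording is over-parameterised if random time is categorical: 12 for 10, or 4 for 2. A reader might infer biased results or a model that cannot be fitted. Neither follows. The marginal covariance and the arm means remain identified, and failure to fit has not been shown. The realistic risks are convergence or non-positive-definite warnings, and an unclear AICC choice because that criterion depends on a parameter count that is itself ambiguous here.

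Dietary intake is one of many secondary measures and does not enter the primary model.

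**What to change.** In SAP 8.3 and the dietary shell in SAP 12.1:

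- Report the arm-minus-placebo differences with 95% intervals at 1, 3 and 6 months whatever the interaction p-value, and name 6 months as the endpoint defined in SAP 4.2.
- Preferably adjust for baseline intake, as protocol 9.3.3 states. Baseline then leaves the response vector and the comparison count becomes 3 × 3 = 9, so the multiplicity sentence needs the same edit. State how the change-from-baseline rows will then be obtained.
- Keep the interaction test as a descriptive line. With baseline as a covariate it has (4 − 1) × (3 − 1) = 6 degrees of freedom and no longer responds to a difference that is constant over follow-up, which is a further reason not to condition on it.
- Specify one within-subject covariance: an unstructured residual matrix, with compound symmetry as the fallback if it does not converge. Keep site as random and omit the separate subject intercept.

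The cost is a few sentences of SAP text, one shell and simpler code. No new data are needed.
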